3.2 Analysis Populations

The analysis populations are defined in Table 3.2-1.

Table 3.2-1Analysis Populations

Population	Description
Intent-to-treat (ITT) population	Subjects who are randomized and who receive at least one dose of study investigational product will be included in the ITT population and subjects will be analyzed according to their randomized treatment group.
As-treated population	Subjects who are randomized and who receive at least one dose of study investigational product will be included in the as-treated population and subjects will be analyzed according to the highest dose they actually receive.
PK population	The Pharmacokinetics (PK) Population includes all subjects who receive at least one dose of investigational product and have at least one PK sample containing detectable MEDI4920.

3.3 Study Subjects

3.3.1 Subject Disposition and Completion Status

A summary of subject eligibility and randomization as well as treatment group received (including summary of subjects randomized but not treated) will be provided. In addition, disposition of subjects throughout the study with respect to completion of treatment and follow-up will be provided.

3.3.2 Demographics and Baseline Characteristics

Demographic information related to sex, age, race, weight, height, and body mass index (BMI) will be presented by treatment group and for all subjects combined. RA history, including years since onset of symptoms, years since diagnosis, current functional capacity and number of nodules will be summarized by treatment group and for all subjects combined. Previously discontinued RA medications along with the reason for discontinuation will be summarized by treatment group and for all subjects combined.

A summary of baseline disease characteristics will include DAS28 CRP, swollen joint count, tender joint count, Physician's global assessment (MDGA), Patient's global assessment (PGA), CRP, erythrocyte sedimentation rate (ESR), Clinical Disease Activity Index (CDAI), anti-cyclic citrullinated peptide antibody (ACPA) (positive/negative) and rheumatoid factor (RF) (positive/negative).

3.3.3 Investigational Product Exposure

The summary of investigational product exposure will include descriptive statistics for the total number of doses received, total amount of MEDI4920 (mg) administered to each treatment arm and the relative dose intensity. The relative dose intensity is defined as the total amount of MEDI4920 administered throughout the trial divided by the planned total dose.

3.3.4 Concomitant Medications

Concomitant medications for RA and other current co-morbidities will be coded using the current version of AZ-DD and summarized for each treatment group and for all subjects combined by ATC level 1 and preferred term. The background dose of methotrexate and corticosteroids use will also be summarized by treatment group and for all subjects combined.

3.4 Efficacy Analyses

MedImmune MEDI4920

3.5 Patient Reported Outcomes

3.5.1 Patient Global Assessment

The only Patient Reported Outcome (PRO) is the PGA. The analysis of the PGA is described in section 3.4.2.2.

3.6 Pharmacodynamic Endpoint(s) and Analyses

3.6.1.1 Pharmacodynamic Endpoint(s)

A commercially available and validated biomarker panel (Vectra DA) measures 12 biomarkers and combines them into a single score to assess the key mechanisms and

pathways that drive RA disease activity. The biomarker panel includes adhesion molecules, growth factors, cytokines, matrix metalloproteinases, skeletal proteins, hormones and acute phase proteins. The Vectra DA biomarker panel has been demonstrated to be a sensitive objective measure of clinical disease activity, with a strong correlation to DAS28 (CRP). Changes in Vectra DA score are also an objective measure of changes in disease activity, showing a significant correlation to changes in DAS28 (CRP).

3.6.1.2 Analysis of Pharmacodynamic Endpoint(s)

The same MMRM analysis as for DAS28 (CRP) will be repeated with Vectra DA change from baseline at each post-baseline visit as the dependent variable. The analysis will only include the on-treatment assessments.

Plots of Vectra DA and its component biomarkers will be presented with study day on the xaxis and result on the y-axis. The mean with standard error bars will be plotted by dose. If appropriate, the y-axis will be presented with log-spacing.

3.7 Safety Analyses

3.7.1 Adverse Events and Serious Adverse Events

Adverse events (AEs) will be coded by MedDRA version 18.0 or higher and the type incidence, severity and relationship to study investigational product will be summarized. Specific AEs will be counted once for each subject for calculating percentages. In addition, if the same AE occurs multiple times within a particular subject, the highest severity and level of relationship observed will be reported. All treatment-emergent AEs will be summarized overall, as well as categorized by MedDRA System Organ Class and Preferred Term. The placebo subjects from each cohort will be combined for the summaries.

3.7.2 Adverse Events of Special Interest

The following adverse events of special interest (AESIs) have been defined in the protocol:

- Thromboembolic events / bleeding events
- Hepatic function abnormality (meeting the definition of Hy's Law [HL])
- Acute and delayed hypersensitivity reactions including anaphylaxis, immune complex disease and infusion-related reactions
- Infections including serious and opportunistic infections (includes reactivation of latent viral infection [varicella zoster/herpes simplex virus, Epstein-Barr virus/ cytomegalovirus] and tuberculosis)

The AESIs will be identified by medical review of the AEs prior to unblinding the study. All treatment emergent AESIs will be summarized by special interest category and preferred term.

3.7.3 Deaths and Treatment Discontinuations due to Adverse Events

Deaths and treatment discontinuation due to AEs will be summarized and listed by treatment group.

3.7.4 Clinical Laboratory Evaluation

Serum chemistry, hematology, coagulation and urinalysis parameters will be collected in this study, analyzed by central laboratory and will be used to investigate the safety of MED4920.

For continuous variables of laboratory tests, all data at baseline and at each scheduled visit will be summarized by treatment group using descriptive statistics. Changes from baseline to each scheduled time point of post-dose will also be summarized using descriptive statistics. For categorical variables of laboratory tests, the frequency and percentage in each category of the item at baseline and at each scheduled visit of post-dose will be presented for each treatment group.

Boxplots of each laboratory variable by study visit will be presented for each treatment group. The boxplots will contain all the data. The boxes will extend to the limits of the interquartile range and the whiskers will extend to the most extreme observation within 1.5 times the interquartile range from the nearest quartile. The data will be plotted on a logarithmic scale when it improves interpretability of the plot. Reference lines will be included on the boxplots for the limits of the normal range.

Laboratory results will also be summarized by Common Terminology Criteria for Adverse Events (CTCAE) grade by visit for the parameters included in Table 3.7.4-1.

Lab parameter	Toxicity grade	Lab values
White blood cell count $(10^9/L)$	Grade 0	\geq LLN
	Grade 1	\geq 3 - <lln< td=""></lln<>
	Grade 2	$\geq 2 - <3$
	Grade 3	$\geq 1 - <2$
	Grade 4	<1
Platelets (10 ⁹ /L)	Grade 0	\geq LLN
	Grade 1	≥ 75 - <lln< td=""></lln<>
	Grade 2	≥ 50 - <75
	Grade 3	\geq 25 - <50

Table 3.7.4-1 CTC grades

Lab parameter	Toxicity grade	Lab values
•	Grade 4	<25
Lymphocytes (10^9/L)	Grade 0	≥LLN
	Grade 1	≥ 0.8 - <lln< td=""></lln<>
	Grade 2	≥ 0.5 - <0.8
	Grade 3	≥ 0.2 - <0.5
	Grade 4	<0.2
Neutrophils (10^9/L)	Grade 0	≥LLN
	Grade 1	≥ 1.5 - <lln< td=""></lln<>
	Grade 2	≥ 1.0 - <1.5
	Grade 3	≥ 0.5 - <1.0
	Grade 4	<0.5
ALT (IU/L)	Grade 0	≤ULN
	Grade 1	> ULN - ≤3*ULN
	Grade 2	> 3*ULN - ≤5*ULN
	Grade 3	> 5*ULN - <20*ULN
	Grade 4	>20*ULN
AST (IU/L)	Grade 0	≤ULN
	Grade 1	> ULN - ≤3*ULN
	Grade 2	> 3*ULN - ≤5*ULN
	Grade 3	> 5*ULN - <20*ULN
	Grade 4	>20*ULN
Bilirubin (umol/L)	Grade 0	≤ULN
	Grade 1	> ULN - ≤1.5*ULN
	Grade 2	> 1.5*ULN - ≤3*ULN
	Grade 3	> 3*ULN - <10*ULN
	Grade 4	>10*ULN

Table 3.7.4-1CTC grades

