2.1.3 Exploratory Objectives

2.2 Study Endpoints

2.2.1 **Primary Endpoints**

- 1. The incidence of AEs and SAEs.
- 2. The incidence of treatment-emergent AEs of special interest (AESIs) as follows:
 - Thrombotic and embolic events
 - Hepatic function abnormality (meeting the definition of Hy's Law [HL]; see Section 5.6.2)
 - Anaphylaxis and serious hypersensitivity reactions
 - Infusion-related reactions

- Immune complex disease
- Serious and/or opportunistic infections (including but not limited to reactivation of latent viral infection [varicella zoster (VZ), herpes simplex virus (HSV), EBV, CMV] and TB)
- 3. Vital signs, laboratory parameters (including coagulation parameters), electrocardiograms (ECGs), and physical examinations.

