4.3.2 Clinical Laboratory Tests

A Laboratory Manual will be provided to the sites that specifies the procedures for collection, processing, storage, and shipment of samples, as well as laboratory contact information, specific to this clinical research study. The Laboratory Manual pertains to samples that will be sent to a licensed central laboratory (ie, samples for clinical laboratory safety tests, PK, immunogenicity, and biomarker analysis).

Clinical laboratory safety tests include serum chemistry, hematology, coagulation, urinalysis, serum pregnancy tests, and other safety tests (as outlined below). Urine pregnancy tests may be performed at the site using a licensed test (dipstick). Clinically significant laboratory results should be repeated as soon as possible (preferably within 24 to 48 hours).

The following clinical laboratory tests will be performed (see Table 4.2.1-1, Table 4.2.2-1, and Table 4.2.3-1).

Serum Chemistry

- Calcium
- Chloride
- Magnesium
- Potassium
- Sodium
- Bicarbonate
- AST
- ALT
- Cholesterol
- IgA, IgG, IgE, IgM, total Ig

Red blood cell (RBC) count

• Erythrocyte sedimentation rate (ESR)

- ALP
- TBL (if result is > 1.5 ULN, indirect and direct bilirubin will be measured)
- Creatinine
- Blood urea nitrogen
- Glucose
- Albumin
- Total protein
- Uric acid
- Triglycerides

Note for serum chemistry: Tests for AST, ALT, ALP, and TBL must be conducted concurrently and assessed concurrently.

Hematology

- White blood cell (WBC) count with differential
 - Hemoglobin

Platelet count

Hematocrit

٠

Coagulation

- International normalized ratio
- Prothrombin time
- Partial thromboplastin time

- D-dimer
- Fibrinogen
- TAT

Urinalysis

- Color
- Appearance
- Specific gravity
- pH
- Protein

- Glucose
- Ketones
- Blood
- Bilirubin
- Microscopy including WBC/high power field (HPF), RBC/HPF

Pregnancy Test (females of childbearing potential only)

- Urine β-hCG
- Serum β-hCG (performed at screening only)

Other Safety Tests

- Hepatitis A antibody (IgM), HbsAg, HbsAb; HbcAb, hepatitis C antibody, hepatitis B virus DNA copy number (assessed at screening only)
- HIV-1 antibody, HIV-2 antibody (assessed at screening only), sample for collection and retention for CMV and EBV (at screening only)
- Protein S, Protein C, anti-thrombin 3, antiphospholipid antibodies (assessed at screening only)
- TB test (eg, QuantiFERON-TB Gold Test) as per local standard of care guidelines (assessed at screening only)

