4.8.4.2 Analysis of Clinical Laboratory Parameters

Laboratory parameters will be assessed at baseline as well as throughout the study. Frequencies of abnormal laboratory measurements will be presented for each laboratory parameter. Also, laboratory parameters will be assessed by presenting tables containing information related to laboratory shifts from baseline relative to the normal range, as well as descriptively over time.

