3.1.1 Visit windows

Visit windows will be used for all scheduled assessments to allow for by-visit analyses, since not all assessments are performed on the scheduled day. Unless specified otherwise, all efficacy and safety analyses will be based on the analysis visit windows. The actual assessment day will be mapped to the planned study visit following the analysis visit windowing rules below:

• If more than one assessment falls within a visit window, the closest non-missing assessment to the scheduled day will be used in the analysis.

• If two non-missing assessment actual dates are equidistant from the target day, the earlier visit will be used in the analysis.

The visit windows will be calculated by bisecting the scheduled visit days. The lower limit of each window will be the mean of the two adjacent planned study days, rounded up to the nearest integer, except for the first post-treatment visit, which will start at 2. The upper limit of each window will be the mean of the two adjacent planned study days, rounded down to the nearest integer.

Table 3.1.1-1Visit windows for DAS28, CDAI, Joint Counts, Patient
Global Assessment, Physician Global Assessment, CRP
and ESR

Planned study day of visit	Visit window	
1	All assessments prior to the first administration of investigation product	
15	Start of first administration of investigation product – Day 22	
29	Day 23 - 43	
57	Day 44 - 71	
85	Day 72 - 99	
113	Day 100 - 127	
141	Day 128 - 155	
169	Day 156 +	

Table 3.1.1-2 Visit windows for Vectra DA

Planned study day of visit	Visit window	
1	All assessments prior to the first administration of investigation product	
15	Start of first administration of investigation product – Day 22	
29	Day 23 - 43	
57	Day 44 - 71	
85	Day 72 - 99	
113	Day 100 - 141	
169	Day 142 +	

Table 3.1.1-3Visit windows for laboratory assessments

Planned study day of visit	Visit window	
1	All assessments prior to the first administration of investigation product	
8	Start of first administration of investigation product – Day 11	
15	Day 12 - 22	
29	Day 23 - 43	
57	Day 44 - 71	
85	Day 72 - 88	

Planned study day of visit	Visit window
92	Day 89 - 95
99	Day 96 - 106
113	Day 107 - 127
141	Day 128 - 155
169	Day 156 +

Table 3.1.1-3Visit windows for laboratory assessments

Table 3.1.1-4Visit windows for ECGs

Planned study day of visit	Visit window	
1	All assessments prior to the first administration of investigation product	

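### SAP 3.7.4 omits the protocol's laboratory abnormality and shift tables, leaving coagulation without an abnormality count and most unscheduled peaks outside the one graded table

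*SAP*

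**What the plan says.** **Protocol.** Section 2.2.1 places "laboratory parameters (including coagulation parameters" within primary endpoint 3. Section 4.8.4.2 makes two commitments on top of descriptive summaries over time. The first is a count: "Frequencies of abnormal laboratory measurements will be presented for each laboratory parameter". The second is a set of tables on "laboratory shifts from baseline relative to the normal range". Section 4.3.2 makes unscheduled samples likely: "Clinically significant laboratory results should be repeated as soon as possible", preferably within 24 to 48 hours.

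**SAP.** Section 3.7.4 plans by-visit descriptive statistics and changes from baseline for continuous tests, category frequencies for categorical tests, boxplots with normal-range lines, and CTCAE "grade by visit for the parameters included in Table 3.7.4-1". That table covers white cells, platelets, lymphocytes, neutrophils, ALT, AST and bilirubin. Section 3.1.1 says that, unless specified otherwise, "all efficacy and safety analyses will be based on the analysis visit windows", and it sets the selection rule: "If more than one assessment falls within a visit window, the closest non-missing assessment to the scheduled day will be used in the analysis". A tie goes to the earlier assessment. Section 3.7.4 states no exception for the graded table.

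**The concern.** In dose groups of 8 to 12, the useful laboratory safety result is how many subjects at each dose became abnormal, how far they moved, and whether they started normal. The two tables that answer this are in the protocol but not in the SAP. What remains is one by-visit graded table for seven parameters, built on a rule that keeps a single value per window.

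Coagulation is where this matters most. Protocol 1.1.1 recounts that one earlier anti-CD40L antibody was halted for thromboembolic events and another curtailed after one. Section 1.6 lists thrombosis as a potential risk here, and Section 3.1.3 names coagulation tests among the laboratory abnormalities that may lead the Dose Escalation Committee to recommend stopping escalation. A dose-related cluster of moderate D-dimer or thrombin-antithrombin shifts is the kind of finding a shift table is meant to expose.

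**Working it through.** The plan gives no figure to reproduce. The check sets the two documents side by side and then applies the SAP's selection rule to its own windows.

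**1. Planned tables compared**

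| Table | Protocol 4.8.4.2 | SAP 3.7.4 |
|---|---|---|
| Abnormality frequency | Each laboratory parameter | Not listed; CTCAE grade by visit for 7 parameters, category frequencies for categorical tests |
| Shift from baseline against the normal range | Yes | Not listed |
| Descriptive summary over time | Yes | Yes, with boxplots |
| Worst post-baseline value per subject | Not mentioned | Not mentioned |

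**2. Coagulation coverage.** Protocol 4.3.2 collects six tests: INR, prothrombin time, partial thromboplastin time, D-dimer, fibrinogen and thrombin-antithrombin complex. The number in SAP Table 3.7.4-1 is 0 of 6. As continuous tests they receive descriptive statistics and boxplots only.

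**3. Selection rule applied to SAP Table 3.1.1-3, treatment period.** The windows are Days 2–11 (target 8), 12–22 (15), 23–43 (29), 44–71 (57) and 72–88 (85).

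- Days covered: 10 + 11 + 21 + 28 + 17 = 87.
- One scheduled sample per window leaves 87 − 5 = 82 possible days for an unscheduled sample.
- Scheduled draw on target (distance 0): every other day is further away, so 82 of 82 are dropped.
- Scheduled draw one day early: only a sample on the target day wins, because a sample one day late ties and loses to the earlier one. Kept 5, dropped 77 of 82 (94%).
- Scheduled draw one day late: samples on the target day and one day early both win. Kept 10, dropped 72 of 82 (88%).

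The one-day offsets are the visit tolerance in Protocol Table 4.2.2-1.

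**4. Example.** In the Day 23–43 window, an unscheduled sample on Day 36 lies |36 − 29| = 7 days from target. A scheduled sample on Day 28, 29 or 30 lies at most 1 day away and is the one kept. The graded table then counts 0 subjects at the Day 36 grade; a worst-value table would count 1.

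**5. Repeats one or two days later.** Three scheduled offsets (−1, 0, +1) by two lags give six timings. In five, the scheduled value is kept and the repeat dropped. In the sixth (scheduled one day early, repeat one day later on the target day), the repeat replaces the scheduled value even if the scheduled value was the abnormal one.

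**6. What a missed subject could mean.** One subject is 1/12 = 8.3% of the 1500 mg group and 1/8 = 12.5% of the 75 mg group (sizes from Protocol 4.8.2). The documents give no rate of subjects whose only peak falls at a dropped draw. Treating that rate p as an assumption, the chance of at least one such subject among 12 is 1 − (1 − p)^12:

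| Assumed p | 2% | 5% | 10% | 20% |
|---|---|---|---|---|
| Chance of at least one | 22% | 46% | 72% | 93% |

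This shows sensitivity to p; it does not estimate what will happen in this trial.

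**The case against.** A reader might infer that unscheduled peaks and coagulation abnormalities will disappear from the report. The documents do not support that.

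- SAP 3.1 lists all data, and its descriptive statistics include minimum and maximum, so a retained extreme shows at its visit.
- SAP 3.7.4 says the boxplots hold all data, though not whether this overrides the windows.
- Protocol 5.1 makes medically significant laboratory findings adverse events, and SAP 3.7.1 counts these per subject at highest severity. A large ALT rise would also trigger the central laboratory alert in Protocol Appendix 4.
- Thrombotic events are summarised as events of special interest, and committee review during escalation does not depend on these report tables.

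Two further limits also stand. When a scheduled abnormal result triggers the repeat, the scheduled value is usually the one kept, so often only a higher repeat grade is lost. And because Grade 0 is defined by the normal limit, the graded table is itself a one-sided abnormality count for its seven parameters.

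These routes soften the consequence without replacing the missing tables. Protocol 5.1 keeps values judged not significant and needing no intervention out of the adverse event tables, and where there are clinical sequelae the diagnosis is reported instead. Listings, plots and a visit maximum do not give the number of subjects abnormal, or shifted from normal, by dose.

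Finally, SAP Section 1 leaves table templates to a separate programming plan that was not available, and the SAP nowhere withdraws the protocol's commitment. The tables may still be produced. But Protocol 4.8.1 points to the SAP for analysis detail, so that is where they should be specified.

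**Conclusion.** The concern holds as a mismatch between protocol and SAP on a component of a primary endpoint. Both promised tables are absent from SAP 3.7.4; 0 of 6 coagulation tests have an abnormality count in any laboratory table; and the graded table, limited to seven parameters, drops an unscheduled value on 88% to 100% of possible days through Day 85. That range assumes a scheduled sample is present and within one day of target. If it is missing, the unscheduled value is used.

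Three stronger readings are tempting and should not be drawn. Peaks and coagulation abnormalities are not lost everywhere, only from the laboratory count tables. The nearest-day rule is not shown to bias results toward normal: it selects on timing, not on the value, and no rate of unscheduled peaks is given. And Protocol 4.8.4.2 requires shifts from baseline but says nothing of the worst value or of unscheduled results, so the SAP breaches no requirement by lacking a worst-value table.

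The SAP should be corrected. The gap is in reporting, and the data needed to close it are already being collected.

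**What to change.** In SAP 3.7.4:

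1. Restore the abnormality-frequency and shift tables of Protocol 4.8.4.2 for every chemistry, hematology and coagulation parameter, by dose with placebo pooled across cohorts.
2. As an improvement beyond what the protocol requires, add each subject's worst post-baseline CTCAE grade, and the shift from baseline to the worst post-baseline value, using all scheduled and unscheduled results.
3. State that the nearest-to-target rule of SAP 3.1.1 applies to by-visit summaries only, and say whether the boxplots include unscheduled values.

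The cost is some SAP wording and a few extra standard tables. No new sampling or data collection is needed.

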3.7.5 Other Safety Evaluations

3.7.5.1 Vital Signs

Vital sign results will be summarized with descriptive statistics (number of subjects, mean, SD, median, minimum and maximum) at each time point. The changes from baseline will also be summarized with descriptive statistics by post-baseline visit.

3.7.5.2 Electrocardiogram

The overall interpretation of the ECG results (Normal; Abnormal, not Clinically Significant; and Abnormal, Clinically Significant) will be summarized using frequency count and percentages by visit and treatment groups.

